10 SAFETY AND ADVERSE EVENTS

10.1 Definitions

10.1.1 Adverse Event/Adverse Device Effect (AE/ADE)

An **adverse event** (AE) is any untoward medical occurrence that develops or worsens in severity during the course of the study. Intercurrent illnesses or injuries should be regarded as adverse events. A pre-existing condition should be recorded as an adverse event if the frequency, intensity or the character of the condition changes. A clinical laboratory abnormality should be documented as an adverse event if any of the following conditions is met:

- Is not otherwise refuted by a repeat test to confirm the abnormality
- Suggests a disease and/or organ toxicity
- Is of a degree that requires active management

10.1.2 Unanticipated Adverse Device Effect (UADE)

Unanticipated adverse device effect is any serious adverse effect on health or safety, any life-threatening problem or death caused by, or associated with a device, if that effect, problem, or death was not previously identified in nature, severity, or degree of incidence in the application, or any other unanticipated serious problem associated with a device that relates to the rights, safety, or welfare of subjects.

10.1.3 Serious Adverse Event (SAE)

Adverse events are classified as serious or non-serious. A **serious adverse event** is any AE that, in the view of either the investigator or the sponsor, is:

- fatal
- life-threatening
- requires or prolongs hospital stay
- results in persistent or significant disability or incapacity
- a congenital anomaly or birth defect
- an important medical event
- require intervention to prevent permanent impairment or damage

Important medical events are those that may not be immediately life threatening but are clearly of major clinical significance. They may jeopardize the subject and may require intervention to prevent one of the other serious outcomes noted above. For example, drug overdose or abuse, a seizure that did not result in in-patient hospitalization, or intensive treatment of bronchospasm in an emergency department would typically be considered serious.

10.1.4 Adverse Events of Special Interest (AESI)

Newly developed DVT, pulmonary embolism, peripheral nerve palsy, skin ulceration NPUAP category III and IV, limb ischemia due to OsciPulse or IPC device are adverse events of special interest. These events may be related to use of the OsciPulse device and any incidence of these events should be reported to the sponsor.

10.2 Recording and Classification of Adverse Events

While admitted to the hospital and enrolled in the study, the electronic medical record will be screened upon completion of the subject's participation in the study for the presence of adverse events by the [REDACTED] research team. The subject will be questioned about adverse events during the 6-hour Interventional Phase of the study.. Information on all adverse events will be recorded in a timely manner in the appropriate adverse event module of the case report form (CRF) in PennCTMS.

While in-hospital, the [REDACTED] team will assess for the development of adverse events by talking to the clinical team and reviewing the electronic medical record. The development of adverse events will be reported to the principal investigator daily. After discussions with the clinical team it will classify these events as definitely related, probably related, possibly related, unlikely or unrelated to the OsciPulse device or study procedures. Serious adverse events (SAE), will be **reported to the principal investigator (PI) by telephone within 12 hours of the event**. The SAE CRF will be completed within 24 hours and the PI and Medical Director will be notified.

All adverse events occurring during the study period will be recorded. The clinical course of each adverse event will be followed until resolution, stabilization, or until it has been determined that the study intervention or participation is not the cause. Serious adverse events that are still ongoing at the end of the study period will be followed up to determine the final outcome. Any serious adverse event that occurs after the study period and is considered to be possibly related to the study intervention or study participation will be recorded and reported immediately.

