Statistical Methodology	Part1: Device tolerability will be assessed with a questionnaire focused on the comfort of the OsciPulse device. This data will only be used to validate the tolerability of the device for use in Phase 2 so no statistical analysis will be performed. Part 2: Device tolerability will be measured with a subject questionnaire focused on their comfort for both the OsciPulse device and the intermittent pneumatic compression device. The questions will have continuous visual analog scales to gauge responses, and we will use a paired t-test to evaluate the difference in responses between the OsciPulse device and the reference therapy. We will also monitor subject compliance, and venous valve sinus hemodynamics, when feasible, for each device and a paired t test will be used to compare those values.
Safety Evaluations	Part 1: Adverse events will be collected

Part 2: Adverse events will be collected. Expected AEs in this population include VTE, skin ulceration, peripheral nerve palsy, limb ischemia, and falls.

**Data and Safety
Monitoring Plan**

The Sponsor is responsible for monitoring the data quality and the ongoing safety of subjects.

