2.4 Known Potential Risks

The application of mechanical thromboprophylaxis is a standard practice in many populations and is not considered to pose serious health risk. The risks include mild discomfort, interference with sleep and movement, injury due to falling, skin breakdown ulceration, and worsening of leg ischemia in patients with peripheral arterial disease. Risks of serious events including peripheral nerve palsy, circulatory compromise such as limb ischemia, deep vein thrombosis, pulmonary embolism, pressure ulcers (NPUAP category III and IV), and neuropathy is exceedingly rare but may occur as a result of use of intermittent pneumatic compression. Subjects who are at higher risk of such complications (subjects with pre-existing severe peripheral vascular disease or severe edema of lower extremities) will be excluded from the study. Adverse events of special interests are outlined in section [10.1.4](#)

Additional adverse events expected in the target population include, but are not limited to, infection, bleeding, delirium, thrombosis, shock, respiratory failure, kidney injury, liver injury, and death.

All subjects will be monitored for adverse events over the course of the intervention as outlined in Section [10](#).

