7.1 Pre-screening

Part 2 only:

- Medical record review to determine subject eligibility

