8.2 Medical Record Review (Part 2 only)

The Medical Record review will be conducted to provide a description of the enrolled patients to aid in the interpretation of the reported outcomes of the study.

- Height
- Weight
- Admitting diagnosis and co-morbidities related to DVT/VTE risk, including:
Heart Failure; diabetes; known thrombophilic states (protein C, protein S, or antithrombin deficiency; thrombotic thrombocytopenic purpura; hemolytic-uremic syndrome; activated protein C resistance; factor V Leiden thrombophilia, prothrombin gene mutation; antiphospholipid antibody; hyperhomocysteinemia); post-partum status (within 6 months); estrogen therapy (oral contraceptive or hormone replacement); active malignancy (treatment within the past 6 months or palliation); history of malignancy (within the past 5 years, other than non-melanoma skin cancer); paralysis or immobilization of a lower or upper extremity related to stroke or injury before this hospital admission; hospitalization in the past 3 months for any reason (excluding this hospital admission); trauma (including acute spinal cord injury, hip fracture, pelvic fracture, femoral fracture and tibial, fibular, knee or other fractures below knee); recent surgery (in the last 48h); acute stroke (in this index hospital admission); prior DVT or VTE; tumor or malignancy; hospitalization in previous 3 months
- Length of stay
- Use of pharmacological thromboprophylaxis and types of agents if used
- Use of pharmacological anticoagulant/antiplatelet therapy, type, dose
- Injury Severity Score (ISS)

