10.2.2 Relationship of AE to Study

All adverse events (AEs) must have their relationship to the study intervention assessed by the clinician who examines and evaluates the participant based on temporal relationship and his/her clinical judgment. The degree of certainty about causality will be graded using the categories below. In a clinical trial, the study product must always be considered.

- Definitely Related – There is clear evidence to suggest a causal relationship, and other possible contributing factors can be ruled out. The clinical event, including an abnormal laboratory test result, occurs in a plausible time relationship to study intervention administration and cannot be explained by concurrent disease or other drugs or chemicals. The response to withdrawal of the study intervention (de-challenge) should be clinically plausible. The event must be pharmacologically or phenomenologically definitive, with use of a satisfactory re-challenge procedure if necessary.
- Probably Related – There is evidence to suggest a causal relationship, and the influence of other factors is unlikely. The clinical event, including an abnormal laboratory test result, occurs within a reasonable time after administration of the study intervention, is unlikely to be attributed to concurrent disease or other drugs or chemicals, and follows a clinically reasonable response on withdrawal (de-challenge). Re-challenge information is not required to fulfill this definition.
- Possibly Related – There is some evidence to suggest a causal relationship (e.g., the event occurred within a reasonable time after administration of the trial medical device). However, other factors may have contributed to the event (e.g., the participant's clinical condition, other concomitant events). Although an AE may rate only as "possibly related"

soon after discovery, it can be flagged as requiring more information and later be upgraded to “probably related” or “definitely related”, as appropriate.

- Unlikely to be related – A clinical event, including an abnormal laboratory test result, whose temporal relationship to study intervention administration makes a causal relationship improbable (e.g., the event did not occur within a reasonable time after administration of the OsciPulse device) and in which other drugs or chemicals or underlying disease provides plausible explanations (e.g., the participant’s clinical condition, other concomitant treatments).

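### Part 2 schedules no look at the legs before, between or after the two devices, so unreported or late-noticed skin and nerve signs can be missed or not placed in a period

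*Combined protocol and SAP*

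**What the plan says.** **Named risks.** Section 2.4 lists among the risks of mechanical prophylaxis "skin breakdown ulceration, and worsening of leg ischemia in patients with peripheral arterial disease", and adds nerve palsy and limb ischemia as serious but very rare. The study summary states: "Expected AEs in this population include VTE, skin ulceration, peripheral nerve palsy, limb ischemia, and falls". Section 10.1.4 says that "peripheral nerve palsy, skin ulceration NPUAP category III and IV, limb ischemia due to OsciPulse or IPC device are adverse events of special interest"; newly developed DVT and pulmonary embolism are on the same list.

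**Role of safety.** Section 3.1 makes safety and tolerability relative to IPC the primary Part 2 objective, and section 4.6.1 includes safety in the primary endpoint. Section 9.2.2 evaluates safety by totalling the events that occur with each device.

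**How events are found.** Section 10.2: "The subject will be questioned about adverse events during the 6-hour Interventional Phase of the study". The research team also assesses for events "by talking to the clinical team and reviewing the electronic medical record". Section 8.7 is a single sentence on monitoring and gives no method. The Part 2 schedule in section 7 marks adverse event monitoring at screening, hour 3 and hour 6.

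**What is measured at the bedside.** Vital signs, height and weight at screening, and an ultrasound of venous flow when feasible. Sections 7.2, 7.3.2 and 7.3.3 add no skin or neurovascular check. The questionnaire (section 8.6) covers comfort, noise, and interference with sleep and movement, plus compliance and preference; no skin or nerve item is named.

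**The concern.** Three of the named harms (skin ulceration, nerve palsy, limb ischemia) would show on the leg. Both devices are worn on the same subject's legs within one 6-hour session, and no washout is stated. A per-device count therefore needs two things of each sign: that it is found, and that it is known to have appeared before the study, in period 1 or in period 2.

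The planned sources give both when the subject or the clinical team notices and mentions a sign promptly. They give neither for a sign that is silent, and they give no timing for one first seen at the end. Section 5.2 does not exclude subjects with reduced leg sensation, and for them self-report may be weakest. At stake is what a result of no events would mean: legs checked and nothing found, or nothing mentioned.

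**Working it through.** **1. Which contacts include a look at the legs?**

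| Contact in Part 2 | What the protocol requires | Leg inspection recorded? |
|---|---|---|
| Screening and enrollment (7.2, schedule) | Consent, eligibility review, record review, vital signs, randomization, AE monitoring | None stated |
| First device, to hour 3 (7.3.2, schedule) | Device, ultrasound when feasible, questionnaire, AE and compliance questions | None stated |
| Second device, to hour 6 (7.3.3, schedule) | Same, with the other device | None stated |

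**2. What do the plan's own rules need?**
- Section 9.2.2 counts events by device, so each event must be placed in a period.
- Section 10.1.1 treats a change in a pre-existing condition as an adverse event. For leg skin, a change can be judged only against a recorded starting state.
- Section 10.2.2 has causality "assessed by the clinician who examines and evaluates the participant based on temporal relationship and his/her clinical judgment". Timing is thus an input to the grade, but the plan has no step that fixes when a leg sign first appeared unless someone reports it.
- Section 10.2 grades relatedness to OsciPulse or to study procedures and does not name the IPC device. The count for the comparator therefore leans even more on timing.
- Section 10.3 ends adverse event reporting at hour 6. Beyond that, section 10.2 provides only for serious events judged possibly related. A minor mark seen later is lost.

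**3. Which signs are affected?**
- Reported at the hour-3 check: in or before period 1. Not affected, except that a pre-study origin stays open.
- First noticed at hour 6: before the study, period 1 or period 2. Cannot be placed.
- Not reported and not charted: missed.

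**4. Scale (illustration only).** The plan's one relevant figure reproduces: section 9.2.3 allows 20 − 6 = 14 evaluable subjects. Each subject wears both devices, so n applies per device. Let p be the true per-device event rate and s the share of events detected. With zero recorded events, the one-sided 95% upper bound solves (1 − p·s)^n = 0.05, so p = [1 − 0.05^(1/n)] / s.

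- n = 20, s = 1: 1 − 0.05^(1/20) = 0.139
- n = 14, s = 1: 1 − 0.05^(1/14) = 0.193

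The documents give no s. Over an assumed range:

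| Assumed s | n = 20 | n = 14 |
|---|---|---|
| 1.00 | 13.9% | 19.3% |
| 0.75 | 18.5% | 25.7% |
| 0.50 | 27.8% | 38.5% |
| 0.25 | 55.6% | 77.1% |

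The first row follows from the sample size alone. The other rows show only that the bound scales as 1/s.

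**The case against.** The strongest reply is that the plan already has safeguards and that inspection would add little.

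- **Events can already be placed.** A reader might infer that no recorded harm can be assigned to a device. The documents do not support that: monitoring is marked at hours 3 and 6, and section 4.2.2 has a questionnaire on tolerability and safety before the second device goes on. This stands, and it limits the point to unreported and late-noticed signs.
- **Baseline screening exists.** Section 7.1 lists "Medical record review to determine subject eligibility", and a reader might conclude that the leg exclusions are judged from the chart alone. But 7.1 is pre-screening; section 7.2 has a separate eligibility review, and section 5.2 gives the attending physician a veto. This stands. What is missing is a recorded starting state of the legs.
- **Who will be enrolled.** Section 8.2 lists "paralysis or immobilization of a lower or upper extremity related to stroke or injury before this hospital admission", which might suggest that such subjects are expected. That section is a list of items to record and also names prior DVT, which section 5.2 excludes. It shows only what will be noted. The supportable statement is that reduced sensation is not an exclusion.
- **The examining clinician in 10.2.2.** An examination triggered by an event need not appear in a schedule, so there is no contradiction. It does, however, start only after something has been noticed.
- **The physical examination was dropped on purpose in V6**, when procedures were updated for the shorter study. A brief look at two lower legs is much narrower and is compatible with that decision.
- **Unseen material.** The description of band fitting is partly redacted and relies on Instructions for Use that are not available here. They might contain a skin check. The visible protocol cites none and requires no record of one.
- **Rare events.** The plan calls the serious events very rare, and 14 to 20 subjects cannot bound a rare rate whatever the detection. This also stands: inspection improves what is observed but does not make a small trial strong evidence of safety.

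**Conclusion.** The point holds in a limited form. As far as the visible protocol shows, Part 2 has no scheduled leg inspection at any of the three contacts where one would be informative, although three of the named harms would show on the leg and safety is counted by device. Silent signs can go unrecorded, and signs first noticed at the end cannot be placed before the study, in period 1 or in period 2.

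Its size cannot be computed from the documents, because they give neither an event rate nor a detection rate. The firm figures are the zero-event bounds at full detection, 13.9% (n = 20) and 19.3% (n = 14). A reader might take one of the wider bounds in the table as the trial's actual uncertainty; those rest wholly on an assumed detection share. Nor does the point cover every named risk: pulmonary embolism and falls are not leg findings, and DVT needs imaging.

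This is a low-cost improvement to safety ascertainment. It does not invalidate the design.

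**What to change.** Add one line to the Part 2 schedule and to sections 7.2, 7.3.2 and 7.3.3. Staff already at the bedside record a brief look at both lower legs (skin marks or breaks, colour, any new numbness or weakness) at three times: before the first device, at the changeover and at final removal.

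State how the record is used:
- A finding at the first check is baseline, and counts later only if it changes (section 10.1.1).
- For a new finding, record the check at which it first appears and count it in the period that ends at that check for the section 9.2.2 tabulation.
- Label that count as period of first appearance. Do not attribute the finding automatically to the device just removed: a delayed mark from the first device may surface only in the second period. Causality stays with the clinician under section 10.2.2.

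If the Instructions for Use already contain such a check, cite it in the protocol and capture the result on the CRF.

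Cost: a minute or two at three existing contacts, one CRF line, and a few more minor marks recorded for both devices. No treatment rule changes.

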10.2.1 Severity of Event

The following guidelines will be used to describe severity.

- Grade 1 (Mild): Awareness of symptoms that are easily tolerated, causing minimal discomfort and not interfering with everyday activities.
- Grade 2 (Moderate): Sufficient discomfort is present to cause interference with normal activity.
- Grade 3 (Severe): Extreme distress, causing significant impairment of functioning or incapacitation. Prevents normal everyday activities.
- Grade 4: Life threatening or disabling adverse event.
- Grade 5: Death related to the adverse event.

10.2.2 Relationship of AE to Study

All adverse events (AEs) must have their relationship to the study intervention assessed by the clinician who examines and evaluates the participant based on temporal relationship and his/her clinical judgment. The degree of certainty about causality will be graded using the categories below. In a clinical trial, the study product must always be considered.

- Definitely Related – There is clear evidence to suggest a causal relationship, and other possible contributing factors can be ruled out. The clinical event, including an abnormal laboratory test result, occurs in a plausible time relationship to study intervention administration and cannot be explained by concurrent disease or other drugs or chemicals. The response to withdrawal of the study intervention (de-challenge) should be clinically plausible. The event must be pharmacologically or phenomenologically definitive, with use of a satisfactory re-challenge procedure if necessary.
- Probably Related – There is evidence to suggest a causal relationship, and the influence of other factors is unlikely. The clinical event, including an abnormal laboratory test result, occurs within a reasonable time after administration of the study intervention, is unlikely to be attributed to concurrent disease or other drugs or chemicals, and follows a clinically reasonable response on withdrawal (de-challenge). Re-challenge information is not required to fulfill this definition.
- Possibly Related – There is some evidence to suggest a causal relationship (e.g., the event occurred within a reasonable time after administration of the trial medical device). However, other factors may have contributed to the event (e.g., the participant's clinical condition, other concomitant events). Although an AE may rate only as "possibly related"

soon after discovery, it can be flagged as requiring more information and later be upgraded to “probably related” or “definitely related”, as appropriate.

- Unlikely to be related – A clinical event, including an abnormal laboratory test result, whose temporal relationship to study intervention administration makes a causal relationship improbable (e.g., the event did not occur within a reasonable time after administration of the OsciPulse device) and in which other drugs or chemicals or underlying disease provides plausible explanations (e.g., the participant’s clinical condition, other concomitant treatments).
- Unrelated – The AE is completely independent of study intervention administration, and/or evidence exists that the event is definitely related to another etiology. There must be an alternative, definitive etiology documented by the clinician.

10.3 Reporting of Adverse Events, Adverse Device Effects and Unanticipated Problems

The PI must conform to the adverse event reporting timelines, formats and requirements of the various entities to which they are responsible.

If the report is supplied as a narrative, the minimum necessary information to be provided at the time of the initial report includes:

• Study identifier• Subject number• A description of the event• Duration (start and end dates)• Expectedness• Action taken	
• Severity Grade• Relationship to study treatment or process• Current status• Whether study intervention was discontinued• Whether the event is serious and the reason why the event is classified as serious• Investigator assessment of the association between the event and study intervention
-------------------------------------------------------------------------------------------------------------------------------------------------------------------------------------------------------------------------	-------------------------------------------------------------------------------------------------------------------------------------------------------------------------------------------------------------------------------------------------------------------------------------------------------------------------------------------------------------------------------------------------

Additionally, all other events (unanticipated problems, adverse reactions, unanticipated adverse device effects and subject complaints) will be recorded and reported with respect to institutional and federal policies.

Reporting Period: Adverse events will be reported from the time of informed consent until study completion at 3 hours for Part 1 and 6 hours for Part 2.

The study investigator shall complete an SAE Form and submit to the study sponsor and to the reviewing Institutional Review Board (IRB). The study sponsor is responsible for conducting an evaluation of the event and shall report the results of such evaluation to the FDA Center for Device and Radiologic Health (CDRH) and to all reviewing IRBs and participating investigators per the applicable regulation.

